9.2.1 Radiologically confirmed pneumonia

Radiologically confirmed pneumonia will be defined as patients in whom the treating physician clinically suspected pneumonia who meet the following 2 criteria:

1. Has a radiologic finding that is consistent with pneumonia (e.g., pleural effusion, increased pulmonary density due to infection, the presence of alveolar infiltrates [multilobar, lobar or segmental] containing air bronchograms); **AND**
2. Illness involves ≥ 2 of the following signs or symptoms:
 - a. fever ($>38.0^{\circ}\text{C}$) within 24 hours before enrolment
 - b. hypothermia ($<35.5^{\circ}\text{C}$) within 24 hours of enrolment
 - c. chills or rigors
 - d. pleuritic chest pain
 - e. new or worsening cough
 - f. sputum production
 - g. dyspnea (shortness of breath)
 - h. tachypnea (respiratory rate $>20/\text{min}$) documented by healthcare professional
 - i. malaise
 - j. abnormal auscultatory findings suggestive of pneumonia (crepitations/rales or evidence of pulmonary consolidation including dullness on percussion, bronchial breath sounds, or egophony).

9.2.2 Lower respiratory tract infection

Lower respiratory tract Infection will be defined as enrolled subject with one of the following:

1. Final clinical diagnosis consistent with LRTI (ie, pneumonia or other LRTI); **OR**
2. Positive laboratory test for pneumococcus, RSV, SARS-CoV-2 or any other infectious respiratory pathogen; **OR**
3. Evidence of both:
 - a. Active infection, ie at least 1 of the following conditions: reported fever, reported chills, measured temperature of $>38.2^{\circ}\text{C}$ or $<35^{\circ}\text{C}$, or an abnormal white blood cell count or differential) **AND**
 - b. Lower respiratory tract disease (at least 1 of the following conditions: abnormal breath sounds, documented tachypnea, cough, sputum production, or dyspnea)

9.2.3 Cardiovascular events following pneumonia

The rates of cardiovascular events at 30 days following pneumonia will be compared to rates among controls without acute LRTD in the 2 months prior to their enrollment. In addition, a group of comparable persons based on age, Charlson co-morbidity index and underlying disease will be assembled through analysis of anonymized health data to assess the rate of these outcomes in this population with pneumonia. Full details will be provided in the SAP.

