3.3 Exploratory objectives

3.3.1 *S. pneumoniae* exploratory objectives

1. To describe the occurrence of cardiovascular events within 30 days of hospitalization for pneumonia for standard-of-care pneumonia diagnosis and radiologically-confirmed CAP only (overall, pneumococcal only, PCV13-type, and PCV20-type) including the following events: non-ST elevation myocardial infarction (NSTEMI), ST-elevation myocardial infarction (STEMI), cerebrovascular accident, new episode of atrial fibrillation or other significant cardiac arrhythmia; deep venous thrombosis or pulmonary embolism, new or worsening congestive heart failure, and cardiovascular-related death.
2. To describe time trends in population-based incidence rates of pneumococcal-related hospitalizations during and after COVID 19 pandemic

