Enhanced Diagnostic Testing. Patients who meet all inclusion criteria and no exclusion criteria with informed consent will be enrolled in enhanced diagnostic testing portion of the study. At the time of their enrolment visit, participants will be interviewed (if possible) and a urine for pneumococcal testing and a swab for respiratory pathogen testing will be obtained in all participants (unless refused at time of collection or the patient's clinical status prevents collection, e.g. an anuric participant cannot provide urine). Aliquots from the urine specimens collected from study participants will be frozen and stored for subsequent shipment to Pfizer laboratories for urinary serotype-specific antigen detection (UAD) and BinaxNOW® testing. Additional testing may be conducted on these specimens or portions of these specimens that may be stored at the Bristol Biobank only after obtaining appropriate permissions.

All LRTD events will have additional information collected at 30 days. Additional information on the participants' final clinical diagnosis, vital status, and cardiovascular complications of their current illness (pneumonia patients only) will be collected.

Study duration. The study is expected to enrol for three consecutive years with an option to extend should additional epidemiological data be needed. Yearly or seasonal interim analyses may be conducted.

Serology subset. All participants in the enhanced diagnostic testing group will be offered participation in the serology subset, which will involve the following additional visits/procedures: 1) serology specimen at enrolment visit/V1 (may be salvaged from SOC specimen if appropriate specimen available), and 2) additional in-person visit at Day 42 to collect a blood specimen for convalescent serology and possibly another respiratory pathogen swab (the later only if another intercurrent acute respiratory illness has occurred). Participation will require signature of an annex to the main study informed consent.

UAD and Viral Testing Controls. An additional group of approximately 400 contemporaneous control participants without acute LRTD, comparable by age group and season to subject in the enhanced testing group, will be enrolled participation. These participants will be identified as adults who are:

3. Patients attending outpatient clinics in participating hospitals in specialties other than respiratory or cardiology OR

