4. Patients currently admitted at participating hospitals on non-medical wards with no current acute respiratory or cardiovascular conditions.

Control participants will provide urine for UAD and BinaxNOW testing and an upper respiratory swab sample for RSV/respiratory pathogen testing. UAD testing will help inform cut points for UAD positivity in this population.

COVID-19 VE assessment is described in Appendix 1.

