7.2 Consented arm, Visit 2: Final diagnosis/Vital status assessment (Day 30)

The assessment may be completed 30 to 45 days after enrolment by phone call, medical record review, during a follow-up standard care visit and/or other means.

At day 30 after admission, the following will be assessed and recorded in the CRF:

- Record final clinical/standard-of-care diagnosis for qualifying acute LRTD illness
- Vital status (alive or deceased) at Day 30 after enrolment
- Cardiac complications through Day 30 after enrolment

The Principal Investigator or designee should make an assessment of final standard -of-care LRTD-related diagnosis if any discrepancy exists in the record. The Investigator is to also confirm, based on any existing or new information, if the participant had clinically and radiographically confirmed pneumonia.

7.2.1 Data collection at V2:

- Record RRIs
- Hospital-related adverse events (e.g., falls in hospital and hospital-acquired infections)
- Final standard of care/ clinical diagnosis of acute LRTD illness
- Vital status at Day 30
- Occurrence of cardiovascular events within 30 days of illness onset (pneumonia only):

- non-ST elevation myocardial infarction (NSTEMI)
- ST-elevation myocardial infarction (STEMI)
- cerebrovascular accident
- new episode of atrial fibrillation or other clinically significant arrhythmia
- deep venous thrombosis or pulmonary embolism
- new or worsening congestive heart failure
- cardiovascular-related death

7.3 Consented arm, Visit 3 [serology subset only]: Convalescent serology assessment on Day 45

For those enrolled in the Serology subset who have signed the related ICD Annex, a follow-up visit will be conducted approximately 45 days after enrolment (visit window: Day 22 – 60). If there is a low patient return rate for this follow-up visit, the study will consider whether home visits may be more convenient and better suited to patients in this study. If home visits are undertaken, they will be offered to participants as a visit option, and an appropriate time will be arranged after liaison between the participant and research team. The procedures undertaken during home visits will ensure that both study participants and research staff are appropriately protected in line with any Health and Safety regulations (e.g. PPI, sharps bins, etc.).

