8.2 Non-consented Patient Outcome measures

The follow-up information should be collected 1 month after enrolment or when the patient is discharged from hospital (whichever occurs later). At day 30 after admission, the following will be assessed and recorded in the CRF:

- Microbiological investigation results
 - Blood cultures.
 - Respiratory microbiology testing, including bacterial (eg, PCR and culture) and viral testing (eg, COVID19, RSV and influenza),
 - Pneumococcal testing (eg, BinaxNOW urine test),
 - Antibiotic resistance results for pneumococcal isolates
 - Sputum Gram stain results
- Hospitalization data:
 - Dates of discharge
 - ICU stay (yes/no)
 - Number of days in ICU
 - Mechanical ventilation and days of ventilator use
 - Requirement for new/increased haemofiltration
 - Non-invasive ventilation requirement and days of usage
- Vital status at Day 30 after enrolment:
 - Deceased, not recovered, recovered, recovered with sequelae, recovery ongoing, unknown
 - Date of death if under 30 days from admission
- Record final clinical/standard-of-care diagnosis for qualifying acute LRTD illness:
 - CAP – radiologically or clinically confirmed, acute bronchitis/LRTI, exacerbation of underlying chronic respiratory disease, LRTI not otherwise specified, congestive cardiac failure, empyema/lung abscess, non-infective process, and non-respiratory infection-related diagnosis.
- Cardiac complications through Day 30 after enrolment:

- ST- and non-ST elevation myocardial infarction, cerebrovascular accident, new episode of atrial fibrillation or other arrhythmia, venous thromboembolism, cardiovascular-related death
- Hospital related adverse events (e.g., falls in hospital and hospital-acquired infections)

The Principal Investigator or designee should make an assessment of final standard-of-care LRTD-related diagnosis if any discrepancy exists in the record. The Investigator is to also confirm, based on any existing or new information, if the participant had clinically and radiographically confirmed pneumonia.

8.3 Non-Consented arms Patient Outcomes: One-year mortality assessment on Day 365

The assessment may be completed 365 to 390 days after enrolment by medical record review, during a follow-up standard care visit and/or other means.

At day 365 after admission, the following will be assessed and recorded in the CRF:

- Vital status (alive or deceased) at Day 365 after enrolment

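### The exploratory cardiovascular comparison in 9.2.3 is biased by its living, backward-observed controls, and the pneumonia side has conflicting start dates and event lists

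*Protocol*

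**What the plan says.** **Comparison.** Protocol 9.2.3 takes the 30-day cardiovascular event rates in pneumonia patients and says that they "will be compared to rates among controls without acute LRTD in the 2 months prior to their enrollment". It also plans a second group from anonymised health data, comparable on age, Charlson index and underlying disease, and leaves full details to the SAP.

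**Controls.** Section 4.1 describes about 400 controls, comparable with the enhanced-testing group by age group and season. They are either "Patients attending outpatient clinics in participating hospitals in specialties other than respiratory or cardiology" or "Patients currently admitted at participating hospitals on non-medical wards with no current acute respiratory or cardiovascular conditions". Section 4.4.4.1 requires each control to sign consent personally. Table 3 (6.3.4) has the interview cover cardiovascular events in the previous 2 months, and its footnote sends the reader to Section 6.2 for the events.

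**Start of the 30 days in pneumonia patients.**
- 3.3.1: "To describe the occurrence of cardiovascular events within 30 days of hospitalization for pneumonia"
- 7.2: "Cardiac complications through Day 30 after enrolment" (also in 7.5 and 8.2)
- 7.2.1: "Occurrence of cardiovascular events within 30 days of illness onset (pneumonia only"

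**Events.** Sections 3.3.1 and 7.2.1 list myocardial infarction (both types), stroke, arrhythmia, venous thromboembolism, new or worsening heart failure and cardiovascular death. The lists in 7.5 and 8.2 have no heart failure item and end "new episode of atrial fibrillation or other arrhythmia, venous thromboembolism, cardiovascular-related death".

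**The concern.** The two sides of the contrast differ in the direction of observation, its length, and whether death can be observed at all. A difference between them could therefore arise without any effect of pneumonia. The biases do not all point the same way. Missing deaths and low-risk recruitment create an apparent excess, while a longer control window hides one if rates are read as proportions.

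On the pneumonia side, staff following 7.2.1 and staff following 7.2 or 8.2 would count events over different periods. Staff following 8.2 would not be prompted for heart failure. These are collection rules as well as analysis choices, so a later SAP cannot fully repair them. It cannot recover an event type that was never asked for, nor observe deaths in people who had to be alive to enrol.

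**Working it through.** The protocol gives no event rate, effect size or precision target for this comparison, so there is no stated figure to reproduce. Rates, fatal shares and selection effects below are assumptions.

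**1. Window length.** Two months is about 60.9 days, and 60.9 / 30 = 2.03. With a constant hazard h, risk over t days = 1 − exp(−h·t). If both groups have the same hazard and rates are read as proportions:

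| Assumed 30-day risk | Control risk over 60.9 days | Apparent ratio |
|---|---|---|
| 1% | 2.02% | 0.495 |
| 3% | 6.00% | 0.500 |
| 5% | 9.89% | 0.506 |
| 10% | 19.26% | 0.519 |

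A true doubling of the hazard, with a 30-day control risk of 1%, would show as 1.99% against 2.02%, which is no difference. If rates are per person-time, this fault disappears.

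**2. Survival and selection.** Let f be the share of all listed events that are cardiovascular deaths, and s the proportional deficit in controls caused by where they are recruited. With no true effect and all listed events counted together:
- person-time ratio = 1 / [(1 − f)(1 − s)]
- ratio of proportions ≈ (30 / 60.9) / [(1 − f)(1 − s)]

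| f | s | Person-time | Proportions |
|---|---|---|---|
| 10% | 0 | 1.11 | 0.55 |
| 20% | 0 | 1.25 | 0.62 |
| 30% | 0 | 1.43 | 0.70 |
| 10% | 25% | 1.48 | 0.73 |
| 20% | 25% | 1.67 | 0.82 |
| 30% | 50% | 2.86 | 1.41 |

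Taking steps 1 and 2 together, a null effect could appear as anything from about 0.5 to 2.9, depending on assumptions and on how the rate is expressed.

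**3. Start date.** Sections 3.3.1 (hospitalization) and 7.2, 7.5 and 8.2 (enrolment) are close, because enrolment is targeted within 48 hours of admission. An enrolment clock ends at about day 30 to 32 after admission. Illness onset is different, because section 4.4.1 admits illness of up to 28 days. Days after admission covered by the onset clock = 30 − days ill before admission:

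| Days ill before admission | 0 | 7 | 14 | 28 |
|---|---|---|---|---|
| Days covered after admission | 30 | 23 | 16 | 2 |

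The onset clock also counts pre-admission events that the other clocks exclude.

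**4. Event lists.** Heart failure is in 3.3.1 and 7.2.1 and absent from 7.5 and 8.2. Section 8.2 is the only itemised list for the non-consented arm; Table 2 has just one general line for cardiac complications. Heart failure does appear in 8.2 among the final diagnoses for the qualifying illness, but that is not a 30-day complication. Arrhythmia is limited to significant ones in 3.3.1 and 7.2.1, and is unrestricted in 7.5 and 8.2. For controls, Section 6.2 is the list of data sources and contains no cardiovascular event list.

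**5. Control information.** 400 × 2/12 = 66.7 person-years. At assumed rates of 2, 5 and 10 per 100 person-years, that gives 1.3, 3.3 and 6.7 expected events.

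**The case against.** The objective in 3.3.1 is exploratory and worded as description. Section 9.2.3 says rates and defers detail to the SAP, which may use person-time and so remove the window-length fault. The 400 controls exist mainly to support urinary antigen cut-offs and pathogen prevalence, so few cardiovascular events among them is not in itself an error. The acute cardiovascular exclusion covers current conditions in the inpatient source only, and the exclusions in 4.4.4.2 contain no cardiovascular criterion. A person with an infarction six weeks earlier could be recruited in another clinic. Admission and enrolment nearly coincide, and both admission and onset dates are collected. Section 7.5 may simply condense 7.2.1, and the eCRF is not shown.

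Most of this stands. The window-length bias is conditional on the use of proportions. Recent events are under-represented rather than removed. The 2-day figure is a worst case. The firm gap in the event list is the non-consented arm.

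A reader might infer that no excess from this study could ever be interpreted, or that the pneumonia event rate is itself invalid. The documents do not support either inference. A second comparator is planned, and faults in the controls do not affect a descriptive rate in cases. What the objection does not answer is that living controls cannot contribute deaths, that 7.2.1 contradicts 3.3.1, that 8.2 lacks a listed event, and that the Table 3 reference leads nowhere.

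**Conclusion.** The contrast with the roughly 400 controls is biased as written. Missing cardiovascular deaths alone would give a spurious ratio of 1.11 to 1.43 if 10% to 30% of events are fatal. With an assumed 25% to 50% selection deficit as well, the ratio is 1.48 to 2.86 per person-time. If proportions are used, the unequal windows roughly halve these ratios. The direction of the survival and selection effects follows from the protocol's rules; their size rests on the assumptions.

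Separately, the onset clock in 7.2.1 conflicts with 3.3.1 and covers between 2 (worst case) and 30 days after admission. The event list differs between sections, and the control list is undefined. These inconsistencies need settling even for a purely descriptive rate, because consented and non-consented patients would otherwise be counted differently. The primary incidence objective is unaffected. The second comparator could carry the comparison, but 9.2.3 ties it to a population with pneumonia, so whether that group is free of pneumonia is unclear.

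**What to change.** 1. Use one start date, admission as in 3.3.1, in 7.2, 7.2.1, 7.5 and 8.2.
2. Use the 3.3.1 event list everywhere. Add new or worsening heart failure to 7.5 and 8.2 and to the non-consented eCRF, and use one wording for arrhythmia.
3. Correct the Table 3 footnote to point to that list, and record event dates for controls.
4. In 9.2.3, express rates per person-time or over equal windows, leave cardiovascular death out of the contrast with the living controls, and label that contrast descriptive. With person-time rates the full 2-month look-back can be kept. Cutting it to 30 days would leave 400 × 30/365 = 32.9 person-years instead of 66.7.
5. State whether the health-data group is free of pneumonia. If it is, follow it forward 30 days from an index date and make it the main comparator, including for cardiovascular death.

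The cost is protocol wording, one added eCRF item, event dates on the control form if not already captured, and a narrower stated conclusion from the controls.

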9.2.4 Acute Respiratory Illness (ARI)

The WHO definition of ARI will be used: An acute respiratory infection with: history of fever or measured fever of $\geq 38\text{ C}^\circ$; and cough; with onset within the last 10 days; and requires hospitalization. (https://www.who.int/influenza/surveillance_monitoring/ili_sari_surveillance_case_definition/en/)

9.3 Data analysis

Detailed methodology for summary and statistical analyses of data collected in this study will be documented in a statistical analysis plan (SAP), which will be dated, filed and maintained by the investigators. The SAP may modify the plans outlined in the protocol; any major modifications of primary endpoint definitions or their analyses would be reflected in a protocol amendment.

9.4 Limitations of the research methods

As with any study in humans there is potential for limitations. The methodology used here in recruiting participants, data collection and analyses will seek to minimize these, as listed below.

9.4.1 Denominator

The two hospitals included in the study serve much of the Bristol population. However, there is likely some cross over at the geographical borders, for example with Bath Hospital. It is expected that this may be directional towards Bristol, as both hospitals are tertiary referral centres so individuals may preferentially attend in Bristol rather than Bath, which is a district general hospital. The team will have assessed the degree of such cross over by the analysis phase so that a correction can be factored into the denominator, but this will be by estimation.

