2.2 Patient population

The patients that will be included in the cohort are all adult patients aged ≥ 18 years presenting to NBT and UHBW with clinical features (signs and symptoms) of acute LRTD. This will be determined by assessing all adult patients admitted to these 2 hospitals using the screening algorithm outlined in Section 4.

3 Research questions and objectives

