4.4 Patient selection

4.4.1 Screening inclusion criteria

Patients must meet all the following inclusion criteria to be eligible for enrolment:

1. Aged ≥ 18 years of age
2. Patients with illness with following 2 characteristics:
 - a. Acute illness (i.e., present for 28 days or less); **AND**
 - b. Evidence of acute LRTD:
 - i. Patients with current or suspected COVID-19 or previous proven COVID-19 within last 28 days **OR**
 - ii. Clinical or radiologic diagnosis of pneumonia or an acute LRTI **OR**
 - iii. New onset or worsening of ≥ 2 of following 8 LRTD symptoms or clinical findings:
 1. fever ($>38.0^{\circ}\text{C}$) or hypothermia ($<35.5^{\circ}\text{C}$) before or within 24 hours of enrolment;
 2. pleuritic chest pain;
 3. cough (including nocturnal only);
 4. sputum production or purulence;
 5. dyspnea (shortness of breath) including orthopnea or on exertion only;
 6. tachypnea (respiratory rate $\geq 20/\text{min}$) documented by healthcare professional;
 7. abnormal auscultatory findings suggestive of LRTD (e.g., crackles/rales or evidence of pulmonary consolidation including dullness on percussion, bronchial breath sounds, wheezing, or egophony);
 8. radiologic finding that is consistent with LRTD, including pneumonia, and/or acute congestive heart failure (e.g., pleural effusion, increased pulmonary density due to infection, the presence of alveolar infiltrates [multilobar, lobar or segmental] containing air bronchograms, or interstitial oedema).

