5.2.3 Postcode (to sector level)

Sector level postcode is required to estimate the socioeconomic status of individuals affected with respiratory disease, and to undertake geotemporal analysis of acute LRTD allowing for mathematical modelling of infection. Determining which localities and socioeconomic groups are most at risk of disease and adverse outcomes is important in determining the availability and distribution public health care interventions, including but not limited to vaccination programmes. Furthermore, the potential impact of other interventions designed to modify risk factors such as comorbid disease, environmental factors and access or availability of healthcare resources can be appropriately assessed and provided based on the data provided by this study.

Mathematically modelling disease patterns and spread in time and place allows for better understanding of how disease outbreaks and incidence of disease occurs in a population, and will provide a generalisable model that can be used both within this population and extrapolated to other populations. This will also not only provide better understanding of disease but also provision of better health care resources to reduce disease morbidity and mortality.

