6.2 Data sources

Consent will be obtained to access data relating to outcomes of:

- Radiology tests
- Microbiology tests
- Clinical parameters regarding hospital admission (including co-morbidities, symptom type and duration, admission observations, etc)
- Vaccination status
- Patient treatment (including requirement for ventilation, renal support, etc)
- Patient outcomes (including hospital length of stay, requirement for intensive care, haemofiltration and complications arising from their LRTD).

Consent will also be obtained to record which GP practice the participant is registered with, in order to use this to generate a denominator for incidence calculation.

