9.1 Study size

Expected study size was calculated using both a retrospective coding data from 2018-2019, and a 21-day prospective audit of adult patients admitted to the Acute Medical Unit at NBT. It should be noted that both methods used to calculate estimated patient numbers were conducted in a time period before the COVID-19 pandemic. Both methods calculated an Avon CAP patient cohort approximately 7,000 adult patients per annum at NBT, and assuming all 2 hospital sites have similar patient numbers, the envisaged patient cohort before COVID-19 was 14,000 patients per annum. However, given the COVID-19 pandemic we expect a significantly large sample size, which is likely to approximate 23,000 patients per annum across the 2 sites. Number of adults in surveillance population is approximately 630,000, yielding expected LRTD incidence of >3,600 per 100,000 population annually (3.65 per 100 person years; 95% CI: 3.60 to 3.70).

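### The primary incidence is meant for residents of a defined area, but no residence condition is stated for counted events, and cross-border flow is left to an estimated denominator correction

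*Protocol*

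**What the plan says.** Protocol section 3.1 makes population-based incidence of community-acquired LRTI hospitalisation the primary outcome. Sections 1.5 and 2.1 tie that incidence to the residents of a delineated area, whose population is the denominator.

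The people counted are described by where they are admitted. Section 2.2 states: "The patients that will be included in the cohort are all adult patients aged ≥ 18 years presenting to NBT and UHBW". Section 4.4.1 opens its list with "Patients must meet all the following inclusion criteria to be eligible for enrolment" and then covers age, acute illness and evidence of LRTD. Neither that list nor the exclusions in 4.4.2 mention residence, postcode or GP registration.

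Section 9.4.1 acknowledges cross-over at the borders. It expects this to run towards Bristol because both hospitals are tertiary centres, and it undertakes to assess the extent by the analysis phase "so that a correction can be factored into the denominator, but this will be by estimation".

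Two variables could locate a patient:

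- **GP practice** (section 6.2): "Consent will also be obtained to record which GP practice the participant is registered with, in order to use this to generate a denominator". It is not among the five items that section 5.2 lists for collation without consent.
- **Postcode sector** (section 5.2.3): "Sector level postcode is required to estimate the socioeconomic status of individuals affected with respiratory disease, and to undertake geotemporal analysis". Section 5.2 lists it for collection without consent, and sections 7.1.1 and 8.1.1 use postcode in both arms.

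Section 1.6 says the two arms are combined to estimate incidence. Patients who decline consent appear only in the screening log.

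**The concern.** A population-based rate needs each counted event to come from the population in the denominator. As written, an eligible patient who lives outside the area and is admitted to either Trust is counted, while the denominator describes the area. The Protocol sees the mismatch, but it proposes to repair it on the denominator side and by estimation. Non-resident events could instead be identified directly from a variable already held.

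The rates at stake are the primary outcome and the secondary incidence objectives. Objectives in section 3.2 are broken down by pathogen and risk group, and some by age. Section 3.3 adds time trends. Section 9.4.1 describes one correction and does not say whether it will vary across these strata or over time. Tertiary referral could plausibly differ by risk group, and cross-border flow could change during a pandemic or if the Bath hospital joins the study.

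**Working it through.** **Inputs** (Protocol section 9.1): "which is likely to approximate 23,000 patients per annum across the 2 sites"; "Number of adults in surveillance population is approximately 630,000"; stated result "3.65 per 100 person years; 95% CI: 3.60 to 3.70". The documents give no non-resident share (f) and no share of residents' admissions that go elsewhere (g). Both are assumed below.

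**1. Reproduce the stated rate.**
- Rate = 23,000 / 630,000 = 3.651 per 100 person-years.
- Half-width = 1.96 × √23,000 / 630,000 = 0.047 per 100.
- 95% CI = 3.604 to 3.698. This agrees with the Protocol after rounding.

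**2. Share at which inflow alone matches the sampling error.**
- 0.047 / 3.651 = 0.0129, so f of about 1.3% equals the half-width.
- Measured to the rounded lower limit of 3.60, 1 − 3.60/3.651 gives about 1.4%.

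**3. Inflow only.** Resident rate = 23,000 × (1 − f) / 630,000.

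| f (assumed) | Resident events | Rate per 100 PY | Uncorrected rate too high by 1/(1 − f) − 1 |
|---|---|---|---|
| 1% | 22,770 | 3.61 | 1.0% |
| 2% | 22,540 | 3.58 | 2.0% |
| 5% | 21,850 | 3.47 | 5.3% |
| 10% | 20,700 | 3.29 | 11.1% |
| 20% | 18,400 | 2.92 | 25.0% |

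**4. Inflow and outflow together.** Resident rate = 23,000 × (1 − f) / (1 − g) / 630,000.

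| f | g | Rate per 100 PY |
|---|---|---|
| 5% | 5% | 3.65 |
| 5% | 10% | 3.85 |
| 10% | 5% | 3.46 |
| 10% | 10% | 3.65 |

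Depending on the two shares, the uncorrected rate can be too high, about right or too low.

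**5. What a correct denominator adjustment would do.** Enlarging the denominator to 630,000 / (1 − f) removes the inflow bias in the overall rate: about 663,000 for f = 5% and 700,000 for f = 10%. This requires f to be known, and postcode sector is the direct way to learn it.

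**6. One correction applied to all strata.** Suppose f = 5% overall and ignore outflow. A stratum with its own share f_s is then reported at (1 − 0.05) / (1 − f_s) times its resident rate.
- f_s = 10%: 0.95 / 0.90 = 1.056, so 5.6% too high.
- f_s = 2%: 0.95 / 0.98 = 0.969, so 3.1% too low.

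**7. Coverage of GP practice.** The consented arm targets up to 80% of eligible patients (section 1.6). Even if that is met, the other 20% (0.20 × 23,000 = 4,600 a year on the planning figure) are in the non-consented arm or have declined. For the non-consented arm, GP practice is not on the list of data to be collected.

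**The case against.** The strongest reply is that sections 2.2 and 4.4 define a surveillance cohort that also serves the clinical, outcome and vaccine-effectiveness objectives. On this view a residence filter for the incidence numerator belongs in the SAP, to which section 9.3 defers detail. The limitation is also disclosed, its likely direction is given, and a correction is promised. These points are fair, and a missing filter would not by itself be a finding. What remains is that the Protocol does state its method, an estimated denominator, when a better one is available from data it already collects. Naming the purpose is also a protocol matter. Section 11.2 separates postcode sector from the pseudonymised clinical data, and section 11.3 keeps identifying data out of use unless there is a specific reason.

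A reader might infer several stronger things that the documents do not support:

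- **That the published rate will be inflated.** A correction is planned and a good one would work (step 5). Outflow acts the other way (step 4), and section 9.4.1 itself says the hospitals serve only much of the Bristol population.
- **That the correction cannot be made specific to age, risk group or pathogen.** The Protocol does not say that it will be, but nothing prevents it.
- **That postcode may not be used for residence.** Section 5.2.3 does not name this use, but section 5.2 justifies the item by the study objectives in general.
- **That GP registration is an unsuitable basis.** It would serve if recorded in both arms. Choosing between it and postcode is a design preference.

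The comparison with the quoted interval also has limits. With 23,000 events almost any systematic error exceeds the sampling error. The 3.65 is an approximate planning rate for LRTD, whereas the primary outcome is LRTI and pneumonia.

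**Conclusion.** The point stands in limited form. The target is incidence among residents, no residence condition is stated for counted events, and the stated remedy is an estimated change to the denominator. The GP-practice route does not, as written, cover the pooled cohort. Bias arises if the estimate is wrong or if the non-resident share differs across strata or over time. Its net direction cannot be settled from the Protocol.

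The size is illustrative only. An uncorrected inflow above about 1.3% would outweigh the quoted sampling error, and assumed shares of 5% and 10% give 3.47 and 3.29 against 3.65 before outflow. These figures rest on assumed shares and on approximate planning numbers that the Protocol does not fix as the final denominator. The matter deserves correction because it touches the primary outcome and the data needed are already collected.

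**What to change.** - **Section 9.4.1:** define the incidence numerator as eligible events in patients whose postcode sector at admission lies in a fixed, listed set of catchment sectors. Registration with a listed GP practice is an alternative if that item is recorded in both arms. Take the denominator from the same population by age, sex and year.
- **Section 5.2.3:** add residence classification to the stated purposes of postcode sector. If GP practice is kept as a basis, add it to the list in section 5.2.
- **Non-residents:** keep them in the clinical, outcome and vaccine-effectiveness analyses.
- **Estimated correction:** limit it to residents admitted elsewhere, for example in Bath, and report the rates with and without it.

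The cost is a slightly smaller numerator, one derived flag, some Protocol and SAP wording, and possibly an added purpose in the Section 251 application. Estimation is not removed altogether, since outflow still has to be assessed, but it no longer has to account for inflow.
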